An Online Self-Management Intervention for Patients with Fibromyalgia
– an RCT
Analysis Plan

Baseline Characteristics and Differences

Descriptive statistics (means and standard deviations in case of normally distributed variables or medians and interquartile ranges in case of non-normally distributed variables, and numbers and percentages in case of categorical variables) will be reported for the following baseline characteristics:

- Sociodemographic variables: age, sex, marital and relationship status, education
- Disease- and treatment related variables: medication, duration of fibromyalgia, physical and psychological comorbidities, (previously) received treatments for fibromyalgia
- Other: frequency of internet use, internet use proficiency, extraversion and neuroticism

Differences in baseline characteristics between the intervention group and control group will be examined, and between patients who completed the intervention and those who did not. For continuous outcomes, T-tests or independent samples median tests (when non-normally distributed) will be conducted. For categorical outcomes, χ^2 -tests will be conducted.

Analyses

All main analyses will be carried out following the intention-to-treat (ITT) principles. As linear mixed models are well-suited to handle missing values, missing data from drop-outs will not be imputed. Person-mean imputation will be applied when necessary to calculate scale scores. The analyses will be conducted (1) with the inclusion of covariates (primary analysis), (2) without the inclusion of covariates (sensitivity analysis) and (3) per protocol (i.e., comparing only the patients who completed the intervention with patients in the control group as a sensitivity analysis) with and without the inclusion of covariates.

Main Analyses

To compare changes in primary and secondary outcome variables during the study period between patients in the intervention and control groups, linear mixed models will be fitted using full maximum likelihood estimation. The models will include fixed effects of time as three dummy variables: 'short-term' for baseline vs. post-intervention, 'mid-term' for baseline vs. 6-week follow-up, and 'long-term' for baseline vs. 3-month follow-up. To indicate the effect of the intervention across time, the fixed effects of interactions between group (i.e., intervention or control group) and timepoint will be included as again three dummy variables: short-term*group, mid-term*group, and long-term*group. Finally, the fixed effects of the covariates age (centered) and sex will be included. The models will include random effects of intercept and the addition of random effects of slopes will be tested with Likelihood Ratio Tests (i.e., the difference in -2LL between the alternative model and the null model using a χ^2 distribution). For each model, the variance-covariance matrix leading to the optimal model fit (i.e., the lowest Akaike's Information Criterion) will be selected using restricted maximum likelihood estimation. Values of $p < .05$ (two-tailed) will be considered as significant.

Assumptions

For each final model, the assumptions of normality, homoscedasticity and linearity will be checked by examining Q-Q plots, scatterplots of residuals versus predicted values, and scatterplots of predicted values versus observed values, respectively. In case assumptions are not met, transformations will be applied. Histograms of the residuals will be inspected for outliers. An outlier will be corrected manually if the outlier is a clear result of an error. Otherwise, the influence of an outlier will be examined by comparing results with and without the outlier. If the outlier is influential, a transformation will be applied. If not, the outlier will be retained.

Effect Sizes

Between-group effect sizes will be calculated for each outcome at post-intervention (T2), 6-week follow-up (T3), and 3-month follow-up (T4). Cohen's d effect sizes will be obtained by

performing independent T-tests in SPSS with change scores (compared to baseline) as dependent variables and group as predictor. Effect sizes of 0.2, 0.5, and 0.8 will be considered as small, medium, and large, respectively (Cohen, 1988).

Minimal Clinically Important Improvement

The number and percentage of participants in the intervention and control group that showed minimal clinically important improvement will be calculated for the primary outcome pain coping, defined as an increase of at least 10% on the VAS pain coping scale at T2. This number is in line with previous recommendations on minimal clinically important improvement in VAS pain (Dworkin et al., 2008). Differences in minimal clinically important improvement in pain coping between the intervention and control group will be compared with the χ^2 -test.

Other Study Parameters

Cost-effectiveness

The main research question of the cost-effectiveness analyses is to investigate the cost-effectiveness of the intervention versus standard care from a societal perspective. In order to study the potential efficiency from a societal perspective, both the medical consumption (direct costs) and productivity losses (indirect costs) will be calculated. Quality-adjusted life years (QALYs) will be computed in order to perform a cost-utility analysis. Utilities (EQ-5D) will be based on the mean values for the patients at three occasions (baseline, post-treatment and three months follow-up).

Interim Analysis

Not applicable.

References

Cohen J. *Statistical power analysis for the behavioral sciences*. Hillsdale, N.J.: L. Erlbaum Associates, 1988.

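### Does comparing intervention completers with all controls call for a new label or an added complier-average estimate?

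*SAP*

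**What the plan says.** Under Analyses, the SAP sets the ranking: "All main analyses will be carried out following the intention-to-treat (ITT) principles". The covariate-adjusted version is primary and the unadjusted version is a sensitivity analysis. The third analysis, run with and without covariates, is per protocol, "comparing only the patients who completed the intervention with patients in the control group as a sensitivity analysis". For dropout, "missing data from drop-outs will not be imputed", because the mixed model is relied on to handle it.

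Three other places bear on the point:

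- Baseline Characteristics and Differences plans tests between the randomised groups "and between patients who completed the intervention and those who did not".
- Main Analyses carries the treatment effect in three time-by-group interactions and lists no group main effect. The only covariates are age and sex: "the fixed effects of the covariates age (centered) and sex will be included".
- Cost-effectiveness gives the comparator as standard care: "to investigate the cost-effectiveness of the intervention versus standard care from a societal perspective". On that reading, controls have no programme to complete.

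The SAP does not define completion. The protocol, which was not available for this review, may do so.

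**The concern.** Patients who finish an online self-management programme may differ from those who stop, in ways related to outcome. The control group contains both kinds of patient, while the filtered intervention group contains one. A difference between them may then reflect who completes as well as what completing does.

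The model does not remove this. Age and sex are unlikely to capture the reasons for completion, and the baseline tests of completers against non-completers feed into no model. Without a group main effect, the model takes the two baseline means as equal. Randomisation justifies that for the intention-to-treat comparison but not for completers against all controls.

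What is at stake is interpretation. If the per-protocol effect exceeds the intention-to-treat effect, a reader might credit the difference to finishing the programme. The apparent remedies are to call the analysis non-randomised and exploratory, and to add a complier-average effect that keeps the randomised comparison.

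**Working it through.** The SAP states no figure on this point, so there is none to reproduce. All numerical inputs below are assumptions. Only the structure comes from the SAP: the one-sided filter, the fixed effects and the two-sided 5% test.

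**1. Simple bound.** Let c be the share of the intervention arm that completes, and g the difference in untreated change, in SD, between would-be completers and would-be non-completers. Controls are a mixture of both, so

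bias = (1 − c) × g.

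With n per arm, SE = √[1/(nc) + (1 + c(1 − c)g²)/n]. For n = 100 and no true effect:

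| c | g | Bias (SD) | Two-sided rejection |
|---|---|---|---|
| 0.9 | 0.2 | 0.1 × 0.2 = 0.02 | 5.2% |
| 0.7 | 0.2 | 0.3 × 0.2 = 0.06 | 6.7% |
| 0.7 | 0.5 | 0.3 × 0.5 = 0.15 | 15.9% |
| 0.5 | 0.5 | 0.5 × 0.5 = 0.25 | 29.8% |

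Simulation of 10,000 trials gave 6.6%, 15.7% and 28.2% for the last three rows. The bias is small when completion is high or weakly selective, and material when completion is low and strongly selective.

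**2. The SAP's own fixed effects.** Assumptions: 70 per arm, four visits, 60% completing, compound symmetry with correlation 0.6, no true effect, 4,000 trials, age and sex left out.

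| Completion depends on | Bias (SD) | Rejection |
|---|---|---|
| Observed baseline score | about 0 | 4–5% |
| Stable level, logit 0.5 per SD | 0.06 | 6–7% |
| Stable level, logit 1 per SD | 0.10 | about 9.5% |
| Interim course, correlation 0.3 with the baseline-to-T2 change | 0.07 at T2 | 7–8% |
| Interim course, correlation 0.5 | 0.12 at T2 | 11% |
| That change itself (upper case) | 0.24 at T2 | 32% |

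If the worse-off patients are the ones who persist, the stable-level bias changes sign (−0.06 and −0.10 SD).

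**3. What a complier-average effect would gain.** This estimate is the intention-to-treat coefficient divided by the share completing.

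- *Precision.* Its root mean squared error was 0.226–0.232 SD. The completer comparison had 0.167 and 0.188 (stable level, logit 0.5 and 1) and 0.194 (interim course 0.5, T2). With SDs of 0.229 and 0.156, it has the smaller error only if the completer bias exceeds √(0.229² − 0.156²) = √(0.0524 − 0.0243) = 0.168 SD. In the table above only the upper case does.
- *Partial use.* Take a true effect of 0.40 SD in completers and 60% completing. If non-completers gain 0.1 SD, the estimate is (0.6 × 0.40 + 0.4 × 0.1)/0.6 = 0.28/0.6 = 0.47. If they gain 0.2 SD, it is 0.32/0.6 = 0.53. The error of 0.07 to 0.13 SD is about the size of the bias to be removed.
- *Loss of non-completers.* If the divisor is the completer share among patients with outcome data, losing a share L of non-completers at random returns L times the completer bias. With half lost that is 0.05 of 0.10 SD, and with all lost it equals the completer result. With loss rising 25%, 50% and 75% over T2 to T4 and no selection, this divisor gave 0.39, 0.39 and 0.36 for a true 0.40. Per-visit two-stage least squares gave 0.39, 0.40 and 0.40.
- *Testing.* Its test of no effect essentially repeats the intention-to-treat test.

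**4. A group main effect in the completer model.** This removes the stable-level bias (0.001 SD), with root mean squared error 0.172–0.177. It introduces −0.075 and −0.13 SD if completion follows observed baseline (logit 0.5 and 1), and leaves 0.13–0.16 SD at T2 under the interim course with correlation 0.5. No single specification is best under every mechanism.

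**The case for a change.** The strongest case for a change is that the SAP gives the same label, sensitivity analysis, to two different things. Dropping the covariates keeps the randomised contrast, whereas dropping the non-completers does not, and the SAP never says so. One sentence would mark the difference.

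The complier-average effect also has the better interval. Its bootstrap interval covered 93–94%, against 87–94% for the completer analysis in the selective scenarios at correlation 0.6. In the upper case the completer test rejects 32% of the time with no effect present.

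The description stands: the contrast is not randomised, and a gap between it and the intention-to-treat result cannot be put down to completing the programme. The argument for acting on it is weaker. The contrast is spelled out where the analysis is defined, so a statistical reader can see its nature, and a label alters no estimate. The better coverage costs width, 0.90 against 0.61 SD, and was obtained for a single baseline-adjusted follow-up, not for the four-visit mixed model. The upper case needs completion to follow the very change being measured, which nothing in the SAP suggests.

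**Conclusion.** No change to the plan follows. The completer comparison is open to selection bias, but it is a conventional, disclosed secondary analysis beneath an intention-to-treat primary analysis that it does not touch. The SAP attaches no decision rule to it. A one-sided filter is hard to avoid when the control arm has nothing to complete.

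Under the assumed inputs the bias is about 0 to 0.12 SD in size, of either sign, and reaches 0.24 SD only in the extreme case. The complier-average effect trades this for lower precision and for an assumption of no benefit from partial use, which is doubtful for an online self-management programme. Statisticians could reasonably choose either, so leaving it out is not a fault. Describing the completer result as non-randomised is something the analysts can do when they report it.

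The sizes rest on assumed sample size, completion rate, correlation, selection mechanism and loss. Very low and strongly selective completion would raise the bias, but it would still leave the primary result as it is.

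### Does the per-protocol analysis need a different model because completers and controls may not share the same baseline mean?

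*SAP*

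**What the plan says.** The SAP, under Analyses, makes intention-to-treat with covariates the primary analysis, repeats it without covariates, and adds a per-protocol run with and without covariates, "comparing only the patients who completed the intervention with patients in the control group as a sensitivity analysis". It gives no separate per-protocol model, so the one under Main Analyses applies.

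That section builds the model term by term. "The models will include fixed effects of time as three dummy variables", each contrasting a later visit with baseline. The intervention effect enters through interactions that "will be included as again three dummy variables: short-term*group, mid-term*group, and long-term*group". The list of fixed effects then closes with two covariates: "Finally, the fixed effects of the covariates age (centered) and sex will be included". There is a random intercept, and random slopes are tested. A main effect of group is not mentioned.

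Under Baseline Characteristics and Differences, differences between the arms "will be examined, and between patients who completed the intervention and those who did not". The variables are sociodemographic, disease and treatment related, and a last line reading "Other: frequency of internet use, internet use proficiency, extraversion and neuroticism". No outcome score is among them.

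Under Effect Sizes, Cohen's d at each follow-up comes from independent t-tests on change from baseline.

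**The concern.** With no group main effect, group has no effect at baseline, and the fitted baseline means are equal apart from age and sex. In a randomised comparison that is true by design, and imposing it gains precision. The per-protocol set keeps all controls but only those intervention patients who completed, so equal baselines become an assumption there. The SAP does not state it. It is not among the assumptions to be checked (normality, homoscedasticity, linearity), and the planned completer comparison lists no outcome score and sets completers against non-completers, not against controls.

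If completers start out better or worse than controls, part of a difference between the per-protocol and intention-to-treat results could come from how the model treats baseline, and not from completing the intervention. A reader given only the listed outputs could not tell the two apart.

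**Working it through.** The SAP gives no figure on this point, so there is nothing to reproduce.

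**Inputs.** The fixed effects are the SAP's. Completion rate, gap, correlation and group sizes are not in it and are assumed: 75 per arm, 60% completion (45 completers against 75 controls), outcome SD 1, completers 0.3 SD above non-completers at baseline, and r = 0.4, 0.6 or 0.8. Since the whole intervention arm has the control mean in expectation, g = (1 - 0.60) × 0.3 = 0.12 SD.

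**Formulas.** Let d0 and dt be the completer-minus-control mean differences at baseline and follow-up. With a random intercept only and complete data, generalised least squares gives:

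- model as listed: dt - r × d0
- with a group main effect: dt - d0

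The two differ by exactly (1 - r) × d0.

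**Expected bias with no treatment effect (SD units).** If a stable trait drives completion, the gap persists and dt = g on average. If the observed baseline score drives it, dt = r × g on average.

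| r | Constant gap: as listed | Constant gap: with group term | Baseline-driven: as listed | Baseline-driven: with group term |
|---|---|---|---|---|
| 0.4 | 0.6 × 0.12 = +0.072 | 0 | 0 | -0.072 |
| 0.6 | 0.4 × 0.12 = +0.048 | 0 | 0 | -0.048 |
| 0.8 | 0.2 × 0.12 = +0.024 | 0 | 0 | -0.024 |

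Simulation of 20,000 null trials per cell agrees to within 0.001. For an equal mix of the two mechanisms it gives +0.03, +0.02 and +0.01 for the model as listed, against -0.04, -0.03 and -0.01 with a group term.

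**Against sampling error.** The standard error of the listed model's estimate is sqrt[(1 - r²) × (1/45 + 1/75)] = 0.173, 0.151 and 0.113. The worst-case bias is therefore 0.42, 0.32 and 0.21 of a standard error. A nominal 5% test rejects 7.0%, 6.2% and 5.5% of the time by normal approximation (7.1%, 6.1% and 5.4% simulated). The group term raises the standard error by the factor sqrt[2/(1 + r)], that is by 20%, 12% and 5%.

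**What showing both models would reveal.** In one trial their distance has SD (1 - r) × sqrt(1/45 + 1/75) = 0.113, 0.075 and 0.038. It exceeds 0.1 SD in 47%, 27% and 2% of trials with the assumed gap, and in 38%, 18% and 1% with no gap at all. The distance says little about whether completion was selective.

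**Range.** (1 - r) × g runs from 0.2 × (0.2 × 0.3) = 0.01 SD (80% completion, gap 0.3, r = 0.8) to 0.6 × (0.5 × 0.75) = 0.23 SD (50% completion, gap 0.75, r = 0.4).

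**A bias that neither model removes.** If completers would improve by D more than non-completers without treatment, both estimates carry (1 - completion rate) × D. At 60% completion and D = 0.2 SD this is 0.4 × 0.2 = 0.08 SD, more than the largest entry in the table.

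**The case for a change.** The best case for a change is that a sensitivity analysis exists to be compared with the primary one, that the SAP's list of fixed effects reads as deliberate, and that a few table rows and sentences cost almost nothing. At the upper end of the range, 0.23 SD passes the 0.2 that the SAP itself calls small. Larger figures are possible: 70 completers against 100 controls with a constant 0.3 SD gap give 0.15 SD at r = 0.5 and rejection in 20% of null trials.

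The description of the text stands, and so does the algebra. The case for a change is weaker:

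- The larger figures need strong selection. With 70 of 100 completing, a 0.3 SD gap between completers and controls means 0.3/0.3 = 1.0 SD between completers and non-completers.
- Age and sex, in the adjusted per-protocol run, absorb any constant gap that they explain. The g that matters there is what is left.
- The t-tests on change scores estimate dt - d0, the contrast the group term would give with complete data. The SAP does not say whether effect sizes are computed on the per-protocol set. If they are, the alternative is already on the page, though as Cohen's d.
- The equal-baseline reading is itself an inference. The fixed intercept is not listed either, and the SAP never says that a common baseline mean is intended.

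The absence of baseline outcome scores from the list of characteristics is a real gap, but of the kind that analysts ordinarily fill when they tabulate outcomes by visit.

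**Conclusion.** No change to the plan is needed. The SAP identifies the per-protocol comparison as completers against controls and gives it a supporting role. The constraint on baseline means is harmless for intention-to-treat. In the per-protocol set it amounts to baseline adjustment, which is right if completion depends on the observed baseline score and off by (1 - r) × g if the gap is constant. A group term exchanges one assumption for the other, at a standard error 5% to 20% larger, with no demonstrated gain in freedom from bias.

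Under the moderate assumptions the error is at most about 0.07 SD, below the SAP's threshold for a small effect and under half a standard error. This rests on assumed completion, gap, correlation and sample size, and on a random-intercept structure with complete data. A trial with low completion, strong selection and weak correlation could reach about 0.2 SD.

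When results are written up, it would help the reader to see baseline outcome scores for completers, non-completers and controls, and to have the comparison called non-randomised. That is good reporting practice and does not require the analysis to be altered.

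### The SAP, read literally, bases the group-by-time tests on full maximum likelihood although nothing it plans needs ML; the standard errors come out slightly too small

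*SAP*

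**What the plan says.** The Main Analyses section of the SAP opens with the purpose of the models, comparing change between the two groups on primary and secondary outcomes, and says that for this "linear mixed models will be fitted using full maximum likelihood estimation".

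The mean model is then fixed:
- "The models will include fixed effects of time as three dummy variables";
- three interaction terms, "short-term*group, mid-term*group, and long-term*group";
- "the fixed effects of the covariates age (centered) and sex will be included".

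Two model-building steps follow. For the random part, "the addition of random effects of slopes will be tested with Likelihood Ratio Tests". The variance-covariance matrix with the lowest AIC "will be selected using restricted maximum likelihood estimation". Significance is judged at two-tailed .05.

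The Analyses section adds a run "without the inclusion of covariates (sensitivity analysis" and per-protocol runs with and without covariates. The SAP refers to a final model only under Assumptions, where it names no estimator. It gives no degrees-of-freedom method and no sample size.

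**The concern.** ML estimates the variance components as if the fixed effects were known, so it makes no allowance for having estimated them. Variances, and the standard errors built on them, come out too small. REML makes that allowance.

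The usual reason to accept ML is that REML likelihoods cannot be compared between models with different fixed effects. That reason does not apply here. The random-slope tests and the AIC step each compare models with the same fixed effects, and REML is valid for both. The covariate-free models do have different fixed effects, but they are a separate sensitivity analysis and are not compared with the primary model by likelihood.

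So the plan uses REML for a selection step and, on its literal wording, the more biased estimator for the results. The error always runs the same way, towards declaring significance. It applies to all three group-by-time terms, for every outcome.

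**Working it through.** **Inputs from the SAP.** Four occasions. Three time and three group-by-time terms, no group main effect listed, age and sex; with the intercept (assumed) this makes 9 fixed effects. Two-tailed .05. No imputation of dropouts.

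**Assumptions, because the SAP gives no figures.** Total N of 60, 100 and 200, 1:1 allocation, within-person correlation 0.5, about 10% in the smaller sex category, dropout of 0% or 30%. The SAP has no figure of its own to reproduce.

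**Step 1: approximation.** For a group-by-time contrast the ML/REML standard-error ratio is about r = √((N − 2)/N). If the REML standard error is right, the type I error under ML is 2 × (1 − Φ(1.96 × r)).
- N = 60: r = √(58/60) = 0.983; 1.96 × 0.983 = 1.927; type I error 5.4%.
- N = 100: r = √(98/100) = 0.990; 1.96 × 0.990 = 1.940; type I error 5.2%.
- N = 200: r = √(198/200) = 0.995; 1.96 × 0.995 = 1.950; type I error 5.1%.

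**Step 2: simulation of the 9-parameter model with no true effect, fitted both ways.** ML/REML standard-error ratio for the short-term interaction:

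| N | Random intercept, complete | Random intercept, 30% dropout | Unstructured, complete |
|---|---|---|---|
| 60 | 0.982 | 0.978 | 0.980 |
| 100 | 0.989 | 0.987 | 0.988 |
| 200 | 0.995 | 0.994 | 0.994 |

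Put into the formula of step 1, the ratios 0.978 to 0.995 give a type I error from 5.5% down to 5.1%.

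A separate simulation with unstructured covariance and assumed correlations of 0.5–0.7 looked at the 3-month term. It gave ratios of 0.979 (N = 60) and 0.988 (N = 100) with complete data, and 0.972 and 0.984 with 30% dropout. The 0.972 is the least favourable ratio at these sizes; the formula turns it into 5.7%.

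**Step 3: rejection rates, same critical value for both estimators** (random intercept, complete data, t reference, 4,000 runs).
- N = 60: ML 5.3%, REML 4.8%.
- N = 100: ML 6.0%, REML 5.7%.
- N = 200: ML 5.0%, REML 4.9%.

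Each rate has a Monte Carlo standard error of about 0.3 points, so only the paired difference is informative. From the unrounded rates it is 5.25 − 4.82 = 0.4 points at N = 60, 6.00 − 5.72 = 0.3 at N = 100 and 5.03 − 4.92 = 0.1 at N = 200.

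**Step 4: what is not due to ML.** In the unstructured simulation at N = 60 with complete data, rejection at 3 months was 6.8% under ML and 6.3% under REML. Of the excess of 6.8 − 5.0 = 1.8 points, 6.3 − 5.0 = 1.3 remain after the change of estimator. Only 0.5 points separate the two fits, and those two were judged on slightly different degrees of freedom.

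**The case against.** **The SAP may intend a final REML fit.** It never names the estimator of the final reported model, and REML is mentioned last, so a refit by REML is not excluded. This is fair as far as it goes. But the only sentence that ties an estimator to the group comparison names ML, and an analyst following the text would report ML results. If REML is intended, the text still needs the correction.

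**ML is an accepted and consistent estimator.** True; the choice is not an outright error. The SAP contradicts nothing here, and the bias fades as N grows. What remains is that the plan takes on a bias for which it has no use.

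**The size is minor.** This stands in full. With no sample size in the SAP, material harm cannot be shown from the document.

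**Stronger readings that do not hold.**
- A reader might infer from rates such as 6.8% or 7.5% at 60 patients that ML itself raises the type I error that far. Most of that excess remains under REML (6.3% and 6.5% in the same runs). The 7.5% versus 6.5% pair, with 30% dropout, also used about 60 versus 38 degrees of freedom (critical values about 2.00 versus 2.02) and has a Monte Carlo standard error of about 0.6 points.
- A reader might scale the bias by a larger parameter count, since there are nine fixed effects. Taking √((n − p)/n) with p of 3 to 5 gives 0.957–0.975 at n = 60, which overstates the bias: the complete-data simulations give 0.979–0.982.
- A reader might conclude that every group-by-time p-value is compromised. All are shifted in the same direction, but by an amount that matters only close to .05.

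**Conclusion.** The point holds as a minor one. On its literal wording the SAP rests its group-by-time tests on full ML without needing it. The standard errors are then too small by about 2% at 60 patients, 1% at 100 and 0.5% at 200, slightly more with dropout. The type I error rises by roughly 0.1 to 0.5 points above 5% over that range. The one less favourable figure, about 0.7 points, is for the 3-month term at 60 patients with 30% dropout and unstructured covariance.

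These sizes rest on the assumed sample sizes, correlations and dropout. The direction does not. Smaller sets, including the per-protocol ones if they are small, would sit towards the upper end, but the SAP does not allow their size to be stated. Any further excess at small sizes is a separate degrees-of-freedom issue, on which the SAP is silent.

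**What to change.** In Main Analyses, replace the statement that the models are fitted by full ML with wording such as: *The final reported models are estimated by restricted maximum likelihood, with Kenward-Roger (or, if unavailable, Satterthwaite) degrees of freedom for the group-by-time terms. REML likelihoods are also used for the random-slope comparison, because the fixed effects of the compared models are identical.* The AIC step can stay as it is.

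The degrees-of-freedom clause deals with the small-sample excess that REML alone leaves.

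The cost is a short change of text and an option in the software call. Standard errors become about 1–3% larger at the smaller sizes (1/0.980 = 1.020 at 60 patients with complete data, 1/0.972 = 1.029 in the least favourable case) and about 0.5% larger at 200 (1/0.995 = 1.005). P-values become slightly larger.

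### The covariance structure is chosen from the data by two under-specified steps, and under one permitted reading the long-term (T4) standard error is too small

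*SAP*

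**What the plan says.** All of this is in the Main Analyses section of the SAP.

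- Estimation: "linear mixed models will be fitted using full maximum likelihood estimation".
- Time enters only categorically: "The models will include fixed effects of time as three dummy variables". The treatment effects are the three interactions "short-term*group, mid-term*group, and long-term*group". No group main effect is listed, so the arms share a baseline mean.
- Step 1, random effects: "The models will include random effects of intercept and the addition of random effects of slopes will be tested with Likelihood Ratio Tests". The test uses "the difference in -2LL between the alternative model and the null model using a χ^2 distribution". The degrees of freedom are not given.
- Step 2, covariance: "the variance-covariance matrix leading to the optimal model fit (i.e., the lowest Akaike's Information Criterion) will be selected using restricted maximum likelihood estimation". No candidate structures are listed.

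The section does not define the slopes, say which matrix step 2 concerns, or state the order of the two steps.

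**The concern.** The three group-by-time terms are the trial's main comparison, and their standard errors depend on the covariance model that survives these two steps. A random intercept alone forces one variance and one correlation on all pairs of visits. If correlation falls with the distance between visits, that model credits the baseline with more information about T4 than it has, and with less about T2 than it has. The T4 standard error is then too small and the T2 standard error too large.

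Whether the two steps would detect this depends on points that the SAP leaves open. Two analysts who both follow it could report different standard errors and p-values for the same long-term effect.

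**Working it through.** **Inputs.** From the SAP: four visits, shared baseline mean, three group-by-time terms, two-sided 5% level. The SAP gives no sample size, SD, correlation or dropout rate, so there is no figure of its own to reproduce. Assumed here: equal variances (set to 1), equal visit spacing, complete data, large samples, and the correlations shown below.

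**1. What a wrongly kept random intercept does.** Let r1, r2, r3 be the true correlations at lags 1, 2 and 3. The fitted common correlation tends to the mean of the six pairs:

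r = (3·r1 + 2·r2 + r3)/6

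With a shared baseline mean, the effect at a visit is the group difference at that visit minus r times the group difference at baseline. Apart from a common factor:

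- variance reported by the model: 1 − r²
- true variance: 1 + r² − 2·r·q, where q is the true correlation of that visit with baseline (r1 for T2, r3 for T4)
- SE ratio k = √(reported/true); actual error = 2·[1 − Φ(1.96·k)]

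Example, AR(1) with 0.7: r = (2.1 + 0.98 + 0.343)/6 = 0.5705, so r² = 0.3255.

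- T4: reported 0.6745; true 1.3255 − 2(0.5705)(0.343) = 0.9341; k = √0.7221 = 0.85; error 9.6%.
- T2: true 1.3255 − 2(0.5705)(0.7) = 0.5268; k = 1.13, so the SE is too large; error 2.7%.

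| True correlation by lag | r | k at T4 | T4 error | k at T2 |
|---|---|---|---|---|
| .65/.60/.55 | .617 | 0.94 | 6.6% | 1.03 |
| .65/.55/.45 | .583 | 0.90 | 7.8% | 1.06 |
| .70/.60/.50 | .633 | 0.88 | 8.3% | 1.08 |
| AR(1) .7 | .571 | 0.85 | 9.6% | 1.13 |
| AR(1) .8 | .699 | 0.81 | 11.1% | 1.18 |
| Compound symmetry .6 | .600 | 1.00 | 5.0% | 1.00 |

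The T4 shortfall is therefore 6-19% where correlation decays, and zero under compound symmetry.

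**2. How often the random intercept is kept, by reading.**

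*Dummy slopes with independent variances (3 df, plain chi-square), AIC on the random-effects matrix only.* This model adds unequal variances but no decay of correlation, so the test has little power against decay.

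- Simulation with 400 trials per cell, 40 and 70 per arm: slopes were added in 12-29% of trials under AR(1) .7 and in 3-8% under .65/.55/.45. T4 error was about 8-11%.
- Simulation with 600 trials per cell, AR(1) .7: the random intercept was kept in 92% at 30 per arm and 81% at 60. T4 error was 8.2% and 10.3%; T2 error was 3.3% and 2.2%.
- A large-sample approximation gives higher rates of adding slopes under AR(1) .7: 20%, 38% and 59% at 30, 60 and 100 per arm. By that figure the random intercept is no longer the usual outcome at 100 per arm under strong decay.
- Even when these slopes are added, large-sample T4 error is 5.9-8.4%.

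*Linear slope.* In the 400-trial simulation settings, slopes were added in 78-100% of trials.

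*AIC over residual matrices.* In the same settings the random intercept was chosen in 0-4% of trials, and T4 error matched an unstructured REML fit (about 5-8%).

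*Dummy slopes with a full random-effects matrix.* There are 4 variances + 6 covariances + 1 residual = 11 parameters for a 4x4 matrix with 10 distinct elements. The split between random effects and residual is not identified, but the marginal covariance is, and it is unstructured. A large-sample test (nominal 9 df) keeps it in 98-100% of trials under AR(1) .7. Under .65/.55/.45 it does so in 68% at 50 per arm and 97% at 100.

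**3. Minor contributors.** With a linear slope, replacing the plain chi-square by the boundary mixture lowered retention of the random intercept by only 0 to 9 percentage points. ML instead of REML understates the SE by a further 0.6-1.3%.

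**The case against.** A random intercept, a likelihood ratio test for slopes and an AIC choice under REML form a recognised mixed-model workflow. The AIC sentence is not limited to the random-effects matrix. If it covers the residual matrix, an unstructured candidate may already be in play. With a linear slope, the test usually rejects the random intercept where the harm would be large. Where it often keeps the random intercept (mild decay or a small slope variance), the SE shortfall is only about 6-7%. The SAP does not single out T4, and its only single-visit criterion for pain coping is at T2, where a wrongly kept random intercept errs on the cautious side.

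All of this stands, and it limits the point to one reading. It does not remove it, because the SAP contains no linear time variable, so dummy slopes are the literal reading, and nothing in the text brings the residual matrix into the AIC step.

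Three stronger readings are tempting and are not supported:

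- *That the route often yields a T4 standard error that is too small.* This holds only under the reading above, and the SAP gives no sample size or correlation from which to say how often it would happen here.
- *That the 11-parameter model invalidates inference.* The marginal covariance remains identified.
- *That the plain chi-square or full ML is a main defect.* Both effects are small.

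**Conclusion.** The point holds as a conditional one. The SAP lets the data choose the covariance structure without fixing what the slopes are or which matrix AIC selects, and the validity of the T4 test depends on those two choices.

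With independent dummy slopes and AIC confined to the random-effects matrix, decaying correlation will usually leave a random-intercept model in place at roughly 30-70 per arm. The T4 standard error is then about 6-19% too small (error about 7-11% instead of 5%), and the T2 standard error is about 3-18% too large in the settings tabulated. Under the other readings the effect is small or absent, and under compound symmetry there is none.

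The sizes rest on assumed correlations, equal variances and complete data. This is a worthwhile, inexpensive improvement to the plan. It is not evidence that the long-term result will be wrong.

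**What to change.** Replace the slope tests and the AIC selection with one prespecified model:

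- the same fixed effects as now listed;
- an unstructured 4x4 covariance over T1-T4 (in SPSS MIXED, a REPEATED statement with COVTYPE(UN));
- REML estimation with Satterthwaite or Kenward-Roger degrees of freedom;
- a fixed fallback order if the model does not converge, for example heterogeneous Toeplitz, then heterogeneous AR(1), with robust standard errors.

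If the sponsor prefers to keep the present route, the SAP should at least define the slopes, name the matrix that AIC selects, list the candidate structures and state the order of the steps.

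The cost is SAP wording and one changed command, with no new data or patients. The downside is a few more covariance parameters (10, against 2 for a random intercept plus residual) and possibly slightly wider T4 intervals.
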